7.4.2 Decision to Initiate Part B

No dose escalations are planned in Part B. The dosing will begin only after review of safety data from the first 3 cohorts of Part A indicates no stopping rules (specified in Section 7.4.1.1) are met. The dose for Part B will be the same as that of Cohort 3 of Part A, unless adjustment is required based on the review of available safety and PK data.

7.4.3 Special Treatment Considerations

7.4.3.1 Premedication for Infusions

Premedication for the infusions is not planned. However, if an infusion reaction occurs, appropriate medication may be used as determined by the study investigator(s). If infusion reactions are observed, but review of the data suggests that dose escalation may continue, administration of acetaminophen, 500 to 1000 mg, and/or an antihistamine (such as chlorpheniramine or its equivalent) may be administered orally 30 to 60 minutes prior to the start of infusion for subsequent subjects.

The decision to implement premedication for infusions in subsequent cohorts will be made by the investigator and sponsor and recorded in the study documentation, along with the dose-escalation decision.

Any premedications given will be documented as a concomitant therapy (see Section 7.7).

7.4.3.2 Management of Infusion Reactions

There is a risk of infusion reaction with any biological agent; therefore, all subjects should be monitored closely. Symptoms and signs that may occur as part of an infusion reaction include, but are not limited to: fever, chills, nausea, headache, bronchospasm, hypotension, angioedema, throat irritation, rash, pruritus, myalgia, and dizziness. In the event that a significant infusion reaction occurs, the following guidance should be followed:

- The drug product infusion should be slowed (for example, reduce infusion rate by 50% [for example, an infusion rate of 12 mL/hr becomes 6 mL/hr or slower]) or stopped based on severity and in accordance with the investigator's assessment:
 - if slowed, the infusion should be completed at the slower rate, as tolerated
 - if determined by the investigator that the infusion should no longer continue, no further attempts to dose the subject should be made
- Supportive care will be administered as required
- If it is determined the subject should not receive further doses of study drug, the subject should complete adverse event and other follow-up procedures per Section 2 of this protocol.

Storage samples should be collected for possible immune safety laboratory testing (Section 9.4.5.2).

7.5 Preparation/Handling/Storage/Accountability

The investigator or designee must confirm appropriate temperature conditions have been maintained, as communicated by Sponsor, during transit for all study drug received and any discrepancies are reported and resolved before use of the study treatment.

Only participants enrolled in the study may receive study drug or study materials, and only authorized site staff may supply or administer study drug. All study drug should be stored in an environmentally controlled and monitored (manual or automated) area in accordance with the labeled storage conditions with access limited to the investigator and authorized site staff.

The investigator, institution, or the head of the medical institution (where applicable) is responsible for study treatment accountability, reconciliation, and record maintenance (such as receipt, reconciliation and final disposition records).

Detailed instructions for the preparation and handling of LY3451838 will be provided to the unblinded site pharmacy personnel by the Sponsor.

Vials of LY3451838 are stable and must be stored refrigerated (2°C to 8°C).

7.6 Treatment Compliance

The study drug will be administered at the CRU, and documentation of treatment administration will occur at the site.

7.7 Concomitant Therapy

Subjects on stable concomitant medication at the time of study entry should continue their regular, unchanged dose throughout the study. These medications will be reviewed by the investigator at screening and eligibility will be determined.

Occasional acetaminophen (<2 g/ 24 hours), stool softeners, or medication of topical use without prior consultation with Lilly medical monitor is allowed. Additional drugs are to be avoided during the study unless required to treat an AE, or if used as a premedication prior to infusion.

If the need for other concomitant medication arises, inclusion or continuation of the subject may be at the discretion of the investigator preferably after consultation with a Lilly medical monitor. Any medication used during the course of the study must be documented.

7.8 Treatment after the End of the Study

Not applicable.

8 Discontinuation Criteria

Subjects discontinuing from the study prematurely for any reason must complete adverse event and follow-up procedures per Section 9.2 of this protocol.

8.1 Discontinuation from Study Treatment

Subjects may be discontinued from the study treatment if an SAE occurs during the study drug infusion, or injections irrespective of causality.

Subjects in Part A who discontinue from treatment before infusion end for any reason should complete ED procedures per Section 2 of this protocol, after AE follow up is completed.

Subjects in Part B who discontinue from the treatment before all injections have been completed may be allowed to complete the rest of the study activities (according to the planned Schedule of Activities in Section 2). The decision to allow a subject to complete the study activities should be made jointly by both sponsor and investigator, and only if the reason for discontinuation does not affect the interpretation of the safety and PK/PD data, and continuation of the study activities does not increase risks for the subject. If it is decided that the subject should be discontinued from the study, subject should complete ED procedures according to Schedule of Activities.

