Pharmacokinetics: Plasma LY3451838 PK (e.g., C_{max} , $AUC_{0-\infty}$) will be calculated using noncompartmental methods. Pharmacokinetic parameters will be summarized by dose level using descriptive statistics. Dose proportionality will be assessed. Mean and individual LY3451838 plasma concentration-time curves will be presented. Absolute bioavailability will be calculated based on data from the IV and SC cohorts.

2 Schedule of Activities

Study Schedule Protocol JAH-MC-LAJA – Part A (Intravenous Administration) and Part B (Subcutaneous Administration)

| Study Visit | 1 | 2 | 3 | 4 | 5 | 6 | 7 | 8 | 9 | 10 | 11 | 12 | 13 | 14 | 15 | 16 ^a |
|---|-----|----------------|---------------------------------------|---------------------------------------|-----------------|---|---|--------------------|------------|------------|------------|------------|------------|------------|------------|---------------------|
| Study Day | -28 | -1 | 1 | 2 | 3 | 5 | 7 | 9 (-1 to +2) | 15 (±2) | 22 (±3) | 29 (±3) | 43 (±3) | 57 (±4) | 71 (±4) | 85 (±7) | 141 / ED (±7) |
| Visit Type | S | A | I | I | D | O | O | O | O | O | O | O | O | O | O | O |
| Informed consent | X | | | | | | | | | | | | | | | |
| Medical history | X | | | | | | | | | | | | | | | |
| Height/weight ^b | X | | X | | | | | | | | X | | X | | X | X |
| Medical Assessment ^c | X | X ^d | X | X | X | X | X | X | X | X | X | X | X | X | X | X |
| Neurological examination | X | X ^d | | X | | X | | | | X | | X | | | | X |
| Electrocardiogram ^e | X | X ^d | Predose, 1, 3 h | 24 h (± 90 m) | X | X | X | X | X | X | | X | | X | | X |
| Vital signs ^{f, g} | X | X ^d | Predose, EOI ^h , 1, 3 h | 24 h (± 90 m) | X | X | X | X | X | X | X | X | X | X | X | X |
| Orthostatic BP and pulse rate | | | Predose, 1 h | 24 h | | | X | | X | | X | | | | | X |
| Pregnancy test (urine) | X | X ^d | | | | | | | | | X | | X | | | X |
| Screening tests | X | | | | | | | | | | | | | | | |
| Eligibility review | | X ^d | | | | | | | | | | | | | | |
| Study drug administration | | | X | | | | | | | | | | | | | |
| Hematology and chemistry ⁱ | | X ^d | Predose | X | X | X | X | X | X | X | X | X | X | X | X | X |
| C3, C4, CRP and ESR | X | | Predose | X | | X | | X | | X | | X | | | | |
| Urine analysis | | X ^d | | X | | X | | X | | X | | | | | | |
| PK sample ⁱ | | | EOI ^h , 3, 6, 8, 12 h | 24 h (± 60 m), 36 h (± 60 m) | 48 h (±60 m) | X | X | X | X | X | X | X | X | X | X | X |

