| PACAP sample ⁱ | | | Predose, EOI ^h 6, 12 h | 24 h | 48 h | | X | | X | | X | | X | | X | X |
| Immunogenicity sample | | | Predose | | | X | | X | | X | | X | | X | | X |
| Samples for infusion and hypersensitivity reactions ^j | | | Predose | | | | | | | | | | | | | |
| Non-genetic biomarker sample | | | Predose | | | X | | | | | | | | | | |
| PGx sample ^k | | | Predose | | | | | | | | | | | | | |

| Study Visit | 1 | 2 | 3 | 4 | 5 | 6 | 7 | 8 | 9 | 10 | 11 | 12 | 13 | 14 | 15 | 16 ^a |
|-------------------------|-----|----|---|---|---|---|---|--------------------|------------|------------|------------|------------|------------|------------|------------|---------------------|
| Study Day | -28 | -1 | 1 | 2 | 3 | 5 | 7 | 9 (-1 to +2) | 15 (±2) | 22 (±3) | 29 (±3) | 43 (±3) | 57 (±4) | 71 (±4) | 85 (±7) | 141 / ED (±7) |
| Visit Type | S | A | I | I | D | O | O | O | O | O | O | O | O | O | O | O |
| Adverse events | | | | | | | | | ← X → | | | | | | | |
| Concomitant medications | | | | | | | | | ← X → | | | | | | | |

Abbreviations: A = CRU admission; BP = blood pressure; CRU = clinical research unit; D = CRU discharge; ED = early discontinuation; EOI = end of infusion; h = hour; I = inpatient stay; m = minute; O = outpatient; C3 = total complement C3; C4 = total complement C4; CRP = C reactive Protein; ESR = erythrocyte sediment rate; PACAP = pituitary adenylate cyclase-activating polypeptide; PGx = pharmacogenomics; S = screening.

Note: if multiple procedures take place at the same time point, the following order of the procedure should be used: electrocardiogram, vital signs, and venipuncture. Unless otherwise specified, predose samples may be taken at any time prior to dosing, based on CRU activity schedule.

a in case of early discontinuation/withdrawal, the subject should undergo all Visit 16 activities.

b Height will be collected at Screening only.

c Full medical assessment prior to first dose (on Day -1 or Day 1), discharge, and discontinuation visits. Symptom-driven medical assessment as deemed necessary by the Investigator.

d Day -1 samples/activities could be collected/Performed up to 5 days before the scheduled day of dosing. The medical assessment, neurological examination and eligibility review may be performed pre-dose on Day 1. If screening visit is within 1 week (inclusive) of Day -1, neurological examination, ECG, hematology and chemistry do not need to be repeated.

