5.1 Overall Design

[figure not shown]
Study J1H-MC-LAJA is a first-in-human, Investigator- and subject-blind, placebo-controlled, randomized study in healthy subjects to evaluate the safety, tolerability, and pharmacokinetics of LY3451838.

The study will be comprised of 2 parts: Part A (single ascending dose with IV administration), and Part B (single dose SC administration). Part B of the study will only be initiated if the review of safety and tolerability data from Part A are supportive.

Screening will occur in the 28 days prior to Day 1. Eligible subjects will be assigned sequentially into up to 8 cohorts, and randomly assigned within each cohort to receive LY3451838 or placebo in a 6:2 ratio. Subjects will be followed for safety / tolerability, PK and immunogenicity, and will be discharged from the study approximately 20 weeks after dosing. If the investigator decides not to administer the first dose to a subject or not to enroll a subject on a particular day, the subject may be rescheduled to participate in the study and any procedures performed up to that point may be repeated. Subjects who discontinue from the study (Section 8.2) before its completion are required to complete the early discontinuation (ED) procedures (Section 2) before their discharge from the study.

Figure 5.1.

Illustration of study design for Protocol J1H-MC-LAJA.

Abbreviations: D = day; W = week

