9.4.5.2 Hypersensitivity reactions

Acute and serious hypersensitivity reactions will be assessed and managed as clinically indicated. The clinical information, including examination findings, laboratory testing and treatment for all serious adverse events, including hypersensitivity reactions, will be captured in the EDC.

Non-acute hypersensitivity reactions, including type 3 hypersensitivity reaction will be assessed by clinical presentation. Routine monitoring of vital signs with regular physical examinations, and laboratory testing (including hematology, liver and renal testing, complements C3 and C4, c-reactive protein [CRP] and erythrocyte sedimentation rate [ESR], and urine analysis) will be undertaken to assess for the development of vasculitis, serum sickness and other manifestations of type 3 hypersensitivity reactions.

Stored serum samples for possible immune safety laboratory testing (including, but not limited to: β -tryptase, total IgE, immune-complex testing, and cytokine panel) will be collected for all subjects before study drug administration (Section 2). Additional, unscheduled, stored serum samples for possible immune safety laboratory testing should also be collected approximately 60 to 120 minutes and 4 to 6 weeks after moderate or severe infusion reactions or hypersensitivity reactions.

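### Section 8.1 sends every Part A subject with a stopped infusion to early-discontinuation procedures once AE follow-up closes, with no option to stay and no link to the later reaction samples

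*Protocol*

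**What the plan says.** Protocol Section 8.1 has one rule for each part.

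- **Part A:** "Subjects in Part A who discontinue from treatment before infusion end for any reason should complete ED procedures per Section 2 of this protocol". The sentence goes on to place this after AE follow-up is finished. No alternative is offered.
- **Part B:** a subject with incomplete injections "may be allowed to complete the rest of the study activities". Sponsor and investigator decide jointly, provided the reason for stopping does not compromise interpretation and staying adds no risk.

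ED is an exit step. Section 5.1 says that subjects who leave early "are required to complete the early discontinuation (ED) procedures (Section 2) before their discharge from the study", and footnote a of the Section 2 schedule says "in case of early discontinuation/withdrawal, the subject should undergo all Visit 16 activities".

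For a stopped infusion after a reaction, Section 7.4.3.2 says "the subject should complete adverse event and other follow-up procedures per Section 2 of this protocol". It does not say whether that means the remaining visits or the ED visit, which is also in Section 2.

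Two sections ask for later samples. Under Section 9.4.5.2, stored serum samples "should also be collected approximately 60 to 120 minutes and 4 to 6 weeks after moderate or severe infusion reactions or hypersensitivity reactions". Section 9.6.1 asks for an immunogenicity sample, with drug and PACAP concentrations, 30 days after a drug hypersensitivity reaction.

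**The concern.** In a single-dose study, stopping the infusion does not undo the exposure. The protocol names acute and delayed hypersensitivity, including immune-complex disease, as a potential risk (Section 3.3). It justifies the roughly 20-week period by immunogenicity monitoring during washout (Section 5.4). A subject whose infusion was stopped for a reaction is among those for whom that monitoring matters most, yet Section 8.1 is the rule that can end it early. No reason is given for a stricter rule in Part A, which has the larger doses.

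What is at stake is late ascertainment in that subject: new non-serious AEs, treatment-emergent antibodies and signs of a type 3 reaction. Under Section 9.2.1, investigators need not actively look for events after a subject has discontinued. Replacing the subject restores the number of completers but not these observations.

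**Working it through.** No stated figure needs reproducing, and the study tests no hypothesis. The check compares sections and adds simple day arithmetic.

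**1. Earliest ED date.** Section 9.2 follows an AE until it resolves, stabilizes or is explained, with no minimum. A short reaction can close within days. If an infusion is stopped for a reason other than an AE, there may be no AE to follow.

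**2. Dates of the reaction samples, for a reaction on Day 1.**
- 30 days: Day 1 + 30 = Day 31.
- 4 to 6 weeks: Day 1 + 28 = Day 29 to Day 1 + 42 = Day 43.

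Neither Section 8.1 nor Section 9.2 says that AE follow-up includes these samples.

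**3. What each reading leaves.** The scheduled end is Day 141, 140 days after dosing. Share observed = d/140, where d is days since dosing. Drug remaining = 2^(−d/t½), one-compartment, with the predicted half-life of 12 days (Section 5.4). The range is for assumed half-lives of 8 to 16 days.

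| Exit | d | Share observed | Drug remaining (8 to 16 days) |
|---|---|---|---|
| Day 3 (Section 9.2 alone; mild or non-AE stop) | 2 | 1% | 89% (84 to 92%) |
| Day 31 (after the 30-day sample) | 30 | 21% | 18% (7 to 27%) |
| Day 43 (end of the 6-week window) | 42 | 30% | 9% (3 to 16%) |

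Even if AE follow-up is read to include the samples, exit at Day 43 ends observation 141 − 43 = 98 days, or 14 weeks, early.

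**4. A partial dose can be large.** The 1500 mg infusion takes at least 60 minutes (Section 7.1). At constant rate and minimum duration it delivers 1500/60 = 25 mg per minute, so 10 minutes delivers 250 mg, the whole planned Part B dose.

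**5. How often.** The documents give no stop rate. The Amendment (d) summary in Appendix 9 reports that none of 40 healthy subjects, at doses up to 1000 mg, discontinued because of an AE. The remaining cohort at risk is therefore mainly the six active subjects at 1500 mg. P(at least one stop) = 1 − (1 − p)^6:
- p = 1%: 1 − 0.99^6 = 6%
- p = 3%: 1 − 0.97^6 = 17%
- p = 5%: 1 − 0.95^6 = 26%

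All three rates are assumptions.

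**6. Content of the ED visit.** Section 9.4.5.2 lists "complements C3 and C4, c-reactive protein [CRP] and erythrocyte sedimentation rate [ESR], and urine analysis" among the tests used to look for type 3 reactions. In both the protocol and SAP schedules, the Visit 16 cells are blank for the "C3, C4, CRP and ESR" row and the urine analysis row. The ED visit inherits that omission.

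**7. Not counted.** Numbers of lost antibody or complement samples are left out because the visit columns are not secure. The protocol schedule shows no immunogenicity sample at Visit 15 (Day 85), yet Section 10.3.6 plans an interim analysis on 12-week antibody data. The schedules reproduced in the amendment summaries also mark different visits.

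**The case against.** The strongest reply is that Section 8.1 does not order immediate exit: ED comes after AE follow-up. Section 9.2 expressly requires follow-up of AEs that led to stopping study drug. That is correct, and a reader who infers same-day discharge goes further than the text. The clause still sets no minimum time, and it does not help where there is no AE.

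A reader might also infer that Sections 8.1 and 7.4.3.2 contradict each other. The documents do not support this. The ED visit is part of Section 2, so the follow-up in 7.4.3.2 can be read as including it. The later samples are unscheduled and event-triggered, so they can be taken before ED. Nor does every stopped infusion need them: one is triggered by a moderate or severe reaction, the other by drug hypersensitivity. Because 7.4.3.2 stops infusions according to severity, a reaction that stops one is likely to trigger the 4-to-6-week sample. The Day 3 row therefore fits mainly mild or non-AE stops.

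It is tempting to add harm to dose escalation. The requirement for at least 5 treated subjects with Day 15 data (Section 7.4.1) exists regardless of Section 8.1, and all available data are reviewed. Stopping rule 3 counts subjects, so a second event in a subject already counted adds nothing. Short follow-up inside a crude AE percentage is common to any dropout, and Section 10.2.1 already summarizes extent of participation.

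Part B retention is conditional too, so a subject who reacts there could also be sent to ED.

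These replies narrow the point. They do not supply an option to stay in Part A or a link between the ED date and the samples.

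**Conclusion.** The point holds as a gap. Followed as written, Section 8.1 lets a Part A subject who has received drug leave before the triggered reaction samples and well before the roughly 20-week monitoring is complete. Part B at least permits that subject to stay.

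For a subject who reacts and whose later samples are taken, about 21 to 30% of planned follow-up is observed, with about 18 to 9% of the delivered drug still present. This assumes one-compartment decline and the predicted 12-day half-life. For mild or non-AE stops there is no lower bound on follow-up.

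The chance that the rule is needed is modest: 6 to 26% in the 1500 mg cohort under assumed stop rates of 1 to 5%. Applying those rates to all 36 active Part A subjects would overstate the remaining exposure, given the experience reported up to 1000 mg. Partial mitigations are AE follow-up, SAE collection for 30 days and the event-triggered samples. They do not cover new non-serious events after exit or late antibody responses. The change is worth making mainly because it is cheap.

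**What to change.** 1. **Section 8.1, Part A.** State that a subject who received any study drug continues the Section 2 safety, ADA and PK visits unless the subject withdraws or the investigator judges the visits harmful.
2. **Section 7.4.3.2.** Replace the open reference to Section 2 with *all remaining Section 2 visits*.
3. **Minimum alternative.** If the sponsor prefers exit, give the reason and state that ED takes place only after any triggered 30-day and 4-to-6-week samples.
4. **ED content.** Add C3, C4, CRP, ESR and urine analysis at ED by a footnote limited to early-discontinued subjects. Visit 16 and ED share one column, so filling the cells would add the tests for every completer.
5. **PK.** Flag partial doses in dose-level summaries. SAP Section 11 leaves PK to a third party, so the flag belongs in that party's plan.

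The cost is two text edits, one footnote, attendance by that subject at visits already planned, and partial-dose PK data to flag. The complement, CRP and ESR tests use chemistry or hematology samples (Appendix 5, footnote a) already drawn at Visit 16, so they need no extra blood.
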